## 5.1.2 Primary Outcomes

The co-primary surrogate outcomes selected for the study are a composite of mortality with left ventricular mass measured by cardiac MRI, and a composite of mortality with the SF-36 RAND physical health composite score. Mortality is included in the primary composite outcomes because death is a fundamentally important clinical endpoint, and because incorporating mortality into the co-primary outcomes avoids the risk of biases associated with censoring of deaths. The LV mass and PHC components of the co-primary endpoints satisfy the following criteria which were used in selecting the primary outcomes:

- 1. Biological plausibility that the intervention will influence the parameter;
- 2. The parameter can be assessed in the study population;
- 3. A proven correlation between the parameter and mortality (and/or hospitalization, preferably the former), with a change in the parameter being associated with a change in mortality (and/or hospitalization)
- 4. Hypothesized responsiveness of the parameter to interventional changes;
- 5. Measured reliability and validity (face, construct, and criterion).

Details of these outcomes are provided below.

## (1) Left Ventricular Mass

The change in the left ventricular mass (LVM) from baseline to 12 months will serve as the basis of the first of the two co-primary outcomes. The hypothesized treatment effect of the daily nocturnal

intervention on the mean change in LVM is 15 g. LVM will be assessed by the cine-magnetic resonance imaging (cine-MRI) technique at baseline and at  $12 \pm 2$  months before termination of the study. It is assumed that at least 80% of all study participants will undergo a follow-up cine-MRI examination.

Left ventricular hypertrophy (LVH) is very common in the ESRD population, at the time of dialysis initiation LVH is found in over 80% of patients. Longitudinal studies have shown that LVH is a potent marker of cardiovascular death risk in patients with ESRD [Nakamura, 2002;Paoletti, 2004;Silaruks, 2000;Silberberg, 1989;Stack, 2002;Zoccali, 2001a;Foley, 1995] and thus serves as a good surrogate marker for mortality. Changes in LVM have been associated with clinically relevant differences in outcomes even over a relatively short one-year period [Foley, 2000]. In a recent study a 10% change in LVM correlated with a 22% improvement in all-cause mortality and a 28% improvement in cardiovascular mortality [London, 2001].

The major biological causes for LVH, volume overload and elevated blood pressure, may be positively influenced by increasing the frequency of hemodialysis. Volume overload and hypertension are pathophysiologically connected by expanded extracellular fluid volume which is caused by increased sodium and water retention in ESRD, particularly in patients without significant residual renal function [Lins, 1997;London, 2003;Onesti, 1975]. Furthermore, there is increased arterial stiffness and lack of vascular compliance in uremic patients that manifest both as increased systolic pressures and widened pulse pressures [Chaignon.M, 1981;Horl, 2002;Lins, 1997]. Development of LVH is also influenced by metabolic factors such as hypoalbuminemia, hyperhomocysteinemia, glycation end products, disturbed calcium-phosphate metabolism and secondary hyperparathyroidism [Blacher, 1999;Ganesh, 2001;Moon, 2000;Rostand, 1999;Scharer, 1999;Zoccali, 2001b]. Daily dialysis may affect each of these factors by improving volume control and increasing removal of uremic toxins. Data by Chan et al. in 28 nocturnal HD patients showed that LV mass decreased over 2 years from  $147 \pm 42$  to  $114 \pm 40$  g/m2 (p = 0.004) while a control group of 13 patients on conventional hemodialysis showed no change in LV mass during this same time period. [Chan 2003]

## (2) SF-36 RAND Physical Health Composite (PHC)

The RAND Physical Health Composite (PHC) from the SF-36 will be used to define the second of the two co-primary outcomes for the trial. The short-form 36 (SF-36) is one of the most commonly used instruments to measure patient-reported health related quality of life in the world, and its 36 items making 8 subscales and 2 summary scales (physical and mental components) have been tested extensively for reliability, validity, and responsiveness in HD patients. [Allen, 2002;Beusterien, 1996;Cagney, 2000;DeOreo, 1997;Diaz-Buxo, 2000;Edgell, 1996;Levin, 1993;Merkus, 1997;Meyer, 1994;Rettig, 1997] The survey is well-accepted by HD patients, taking only 5 to 10 minutes to complete. [Kurtin, 1992; Rettig, 1997]. Studies in nocturnal hemodialysis patients have shown an improvement in both PCS and MCS scores from baseline [Brissenden, 1998;Kooistra, 1998;Lockridge, 1999;McPhatter, 1999;Mohr, 1999]. The minimal clinically important difference for a change in each of these scores has been suggested to be 3 to 5 points. [Hays, 2001; Samsa, 1999]

The RAND PHC score is used as a component of a co-primary outcome rather than one of the SF-36 summary scales (PCS, MCS) because the PCS and MCS can in some cases produce distorted results. [Simon, 1998] In one study, for example, the MCS failed to detect major clinical differences associated with disease progression, despite significant differences in its component

subscales. [Norvedt, 2000] The RAND PHC is based on the same SF-36 scales as the PCS score (physical function, role-physical, pain, general health perceptions). Unlike the PCS, however, the scoring algorithm used to calculate the PHC is based on non-orthogonal factor rotation. [Hays, 1998] This allows the PHC to correlate with mental health, unlike the PCS.

Because self-administered questionnaires may be more difficult to complete for the elderly, minority groups, and those with high comorbidity from trial participation [Unruh, 2003], all questionnaires will be administered by trained interviewers using computer-assisted interviewing (CAI). HRQL will be assessed at baseline, 4, and 12 months by interviewers blinded to treatment allocation through a central telephone service.

# 5.1.3 Main Secondary Outcomes

The secondary outcomes of the study are summarized in Table 8 below. Note that the change from baseline to 1 year in the LV mass score, without mortality, will serve as the main secondary outcome for the cardiovascular structure and function domain. In addition, the change from baseline to 1 year in the SF-36 PHC score, without mortality, is the main secondary outcome in the health related quality of life and physical function domain. The details for both of these measures are provided in Section 5.1.2.

# 5.1.3.1 Depression/Burden of Illness (Beck Depression Inventory)

# Main Secondary Outcome:

The 12-month mean change in the Beck Depression Inventory v1 will be used as the main secondary outcome measure.

The Beck Depression Inventory, a 21 question well validated survey presented in multiple choice format, measures the presence and degree of depression in adults. Each of the answers is scored on a 0 to 3 scale, and inventory items correspond to a specific category of depressive symptom and/or attitude. It is frequently used to assess depression in patients with ESRD [Craven, 1988;Kimmel, 1995;Kimmel, 1998;Peterson, 1991;Sacks, 1990], and is associated with mortality in this patient population. [Kimmel, 2000] In addition, it has been previously used in daily HD patients. [Troidle, 2003]. The BDI will be measured at baseline, 4 months and 12 months.

# 5.1.3.2 Cognitive Function (Trailmaking Test B)

# Main Secondary Outcome:

The change from baseline to 12 months in the Trailmaking Test B completion time will be the main secondary outcome to assess cognitive function.

Trailmaking Test B (Trails B) evaluates the ability to visually search, sustain attention, and perform cognitive shifting as the activity is completed. This test is brief, sensitive to subtle neuropsychological impairments, can be compared with age-adjusted norms, and is useful in monitoring the progression of neuropsychological dysfunction. Test-retest reliability, construct validity, and concurrent validity have been previously documented. The Trails B has been used in studies of ESRD and CKD and in patients following kidney transplantation [Kramer, 1996;Kurella, 2004;Umans, 1998]. In addition, this test works well over a wide range of cognitive function and is not subject to floor or ceiling effects.

In the Trails B test, the subject draws lines, connecting 25 circles that contain numbers from 1 to 13 and letters from A to L. The subjects must draw lines alternating from number to letter. The total time to complete the task is recorded. Errors are not counted, but the subject is alerted to mistakes made. They are instructed to correct them which increases the amount of time needed to complete the task. For this trial, Trails B has been selected as the main secondary outcome for evaluation of the cognitive function domain, as it assesses higher order "executive" functions in addition to attention and the skills necessary to complete Trails A. The Trails B test will be performed at baseline, months 4 and 12.

Table 8:	Summary	of Outcome	Measures
----------	---------	------------	----------

Category	Outcome
Co-Primary Outcomes:	
Cardiovascular Structure and Function	Composite of 12 month Mortality and change in Left-Ventricular Mass by Cine-MRI
Health-related Quality of Life and Physical Function	Composite of 12 month Mortality and change in SF-36 Physical Health Composite Score
Secondary Outcomes: ( 9 dom domain)	ains – those in bold are designated as main "priority" outcomes within the
Cardiovascular Structure and	Left-ventricular mass by cine-MRI
Function	End-diastolic, end-systolic, and stroke volumes, ejection fraction, cardiac output
	Rate of intradialytic hypotension episodes
	Interdialytic weight gain
Health-related Quality of	SF-36 Physical Health Composite score
Life/Physical Function	Health Utilities Index score
	Feeling Thermometer score
	Medical Outcomes Study Sleep Scale
	Lower Extremity Performance Battery* score
Depression/Burden of Illness	Beck Depression Inventory, v1 score
Cognitive Function	Trailmaking Test B score
	Modified Mini-Mental Status score
Nutrition and Inflammation	Serum albumin
	Normalized protein catabolic rate
	Body mass index
	Lean body mass by single frequency bioimpedance analysis

Mineral Metabolism	Predialysis serum phosphate
	Predialysis serum calcium
	Calcium-phosphate product
	Parathyroid hormone
	Phosphate binder dose
Survival and Hospitalization	Rate of non-access hospitalizations or death
	Rate of access hospitalizations
	Rate of all hospitalizations or death
	Rate of cardiovascular hospitalizations or death
	Total hospital days (over 12 months)
Hypertension	Average pre-dialysis blood pressure
	Average post-dialysis blood pressure
	Average pulse pressure
	Proportion of patients with wkly average predialysis systolic blood pressure <110 mmHg
	Number of prescribed antihypertensives
Anemia	Pre-dialysis hemoglobin
	Erythropoietin dose
	Cumulative intravenous iron requirements (over 12 months)
	Serum ferritin and transferrin saturation
Adverse Events and Risks:	
Vascular Access Complications	Time to first access intervention
	Rate of access interventions
	Time to first access failure
	Rate of access failures
	Rate of infection related failures
Patient Burn-out	Proportion of patients requiring dialysis modality change over 12 months
	Monthly average number of missed treatments (baseline and monthly)
	Weekly average number of shortened treatments (baseline and monthly)
Treatment Burden:	
Patient Burden	Minutes to recovery
	Proportion of patients wishing to continue, or switch to nocturnal HD at 12 months

\*gait speed, time to stand, standing balance

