## 3. Intervention Plan

## 3.1 Description of the Intervention: Dialysis Frequency and Dose

## 3.1.1 Summary of the Dose Intervention

Consenting patients meeting eligibility criteria will be randomized to 1 of 2 hemodialysis regimens, as shown in Table 4:

i) *Conventional home hemodialysis* of 3 sessions per week. Patients may remain on their usual dialysis prescription subject to a minimum delivered eKt/V of 1.1 per session AND a minimum treatment time of 2.5 hours per session;

ii) Long overnight home hemodialysis of 6 sessions per week, with a minimum treatment time of six hours AND a minimum delivered standard Kt/V (sKt/V) of 4.0

This design is intended to achieve a large separation in a wide range of treatment parameters related to small and middle molecule solute clearance, total weekly treatment time, and ultrafiltration, as shown in Tables 4 and 5.

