## 4. Vanguard Phase

## 4.1 Early Monitoring and Process Adjustments

Because this is the first randomized trial of six-times per week home nocturnal hemodialysis, it is possible that unforeseen obstacles may hamper the ability of the study to accomplish its objectives. Accordingly, the first 12 months of recruitment and follow-up in the trial have been designated as the Vanguard phase of the trial. During this period, automated weekly reports will monitor the progress of the study in achieving the following benchmarks: a) 80 randomized patients within one year of the start of enrollment, b) at least 95% of randomized patients successfully complete the modality specific post-randomization component of the training program for their assigned therapy and initiate home hemodialysis, c) 80% of patients attend at least 80% of scheduled dialysis treatments within each treatment arm, and d) 80% of patients attain 80% of their total prescribed weekly treatment time. If shortfalls in meeting these benchmarks are identified, processes for achieving recruitment and adherence targets will be modified to improve performance. The objective of the Vanguard phase is to identify and correct problems as rapidly as possible to increase the likelihood that the study will achieve its targeted recruitment and adherence goals, and to assure that any protocol changes are implemented very early in the trial so that a stable protocol will be in effect for the majority of the study. After the first year of the trial is completed, the Data Safety and Monitoring Board will review the success of the trial in meeting these benchmarks to determine if the trial should continue to completion. Specific plans for monitoring and implementing adjustments to meet the benchmarks are summarized below.

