nocturnal hemodialysis. If more frequent HD substantially reduces IDHE, this therapy may reduce mortality and other hard CV outcomes. Data will be collected during baseline dialysis sessions prerandomization, while the patient is undergoing 3x/week dialysis, and then during a midweek dialysis session each month. The rate of IDHE will be computed as fraction of reported sessions during which IDHE occurred. Factors associated with IDHE (as identified in the HEMO Study) will be tested to see if they predict IDHE in either group. Subanalyses will include weekly ultrafiltration volume and its dependence on dialysate sodium concentration.

c) Interdialytic Weight Gain. A decrease in interdialytic weight gain has been hypothesized to be one mechanism by which improvements in LV mass can be seen. Thus, interdialytic weight gains will be determined each month for the 48 and 72 hour dialytic interval in the standard arm and for the 24-hour and 48-hour dialytic interval in the nocturnal arm of the trial. The collection of this data will be performed during the same week that the pre-dialysis blood pressure data is collected.

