#### D. Mineral Metabolism and Anemia Measures – see Labs and Medications Table 11C

E. Events (hospitalizations, access complications, survival, discontinuation of the intervention) will be collected throughout follow-up

				•	-								
Measurement	Baseline	1 mo	2 mo	3 mo	4 mo	5 mo	6 mo	7 mo	8 mo	9 mo	10 mo	11 mo	12 mo
Adherence to Therapy													
Number of missed sessions (over 1 month)	~	~	~	~	~	~	~	~	~	~	~	~	~
Number of shortened treatments (over last week)	~				~				~				~
Burden of Treatment													
Minutes to recovery question	~				~								~
Modality preference question	~				~								~
Characterizing the Non-dialytic as	pects of th	ne In	terve	ntior	1								

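### Table 8 measures two of the three burn-out outcomes as raw counts of missed and shortened treatments, although one arm is prescribed twice as many sessions as the other

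*Protocol*

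**What the plan says.** Table 8 lists Patient Burn-out under adverse events and risks, with three measures. The first is the proportion of patients who need a change of dialysis modality over 12 months. The other two are "Monthly average number of missed treatments (baseline and monthly") and "Weekly average number of shortened treatments (baseline and monthly"). Part F of Table 9 collects them in the same form: "Number of missed sessions (over 1 month") and "Number of shortened treatments (over last week").

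Section 3.1.1 sets the two schedules. The control arm receives conventional home hemodialysis "of 3 sessions per week"; the intervention arm receives "Long overnight home hemodialysis of 6 sessions per week". At baseline all patients dialyze three times per week (Sections 2.8 and 5.1.5.1 b).

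Elsewhere the same behavior is measured differently. One Vanguard benchmark in Section 4.1 requires that "80% of patients attend at least 80% of scheduled dialysis treatments within each treatment arm". The paragraph on missed dialysis treatments in Section 4.1, and Section 9.10, speak of a rate or rates of missed treatments and name no denominator.

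**The concern.** A count of missed or shortened sessions depends both on how a patient behaves and on how many sessions there were to miss. Here the number of sessions is fixed by the randomized assignment and differs by a factor of two, so the count does not compare behavior between arms. It also does not compare a nocturnal patient with his or her own baseline, because the schedule doubles at randomization in that arm alone.

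Burn-out is one of the potential risks named in Section 5.3 (item d), and Section 9.10 intends the compliance results to inform the design of a later full-scale trial. If Table 8 is followed as written, patients who keep to nocturnal dialysis as faithfully as controls keep to theirs would appear to tolerate it half as well.

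**Working it through.** **Inputs from the protocol.** 3 and 6 sessions per week (Section 3.1.1); 3 per week at baseline (Sections 2.8 and 5.1.5.1 b); missed treatments counted per month and shortened treatments per week (Table 8 and Table 9 F).

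**Assumption.** The protocol gives no per-session probability p of missing or shortening a treatment. It is taken as equal in both arms and varied from 2% to 20%. The upper end corresponds to a patient exactly at the benchmark of 80% attendance.

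**The plan's own figure.** Table 4 gives the difference in sessions per week as +100%: (6 − 3)/3 = 100%. This is reproduced.

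**Sessions per month.** Weeks per month = 365.25/12/7 = 4.35. Control: 3 × 4.35 = 13.0. Nocturnal: 6 × 4.35 = 26.1.

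**Expected missed treatments per month** = p × sessions per month:

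| p in both arms | Control | Nocturnal | Ratio |
|---|---|---|---|
| 2% | 0.26 | 0.52 | 2 |
| 5% | 0.65 | 1.30 | 2 |
| 10% | 1.30 | 2.61 | 2 |
| 20% | 2.61 | 5.22 | 2 |

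The ratio is 6/3 = 2 whatever p is, provided that p is equal in the arms.

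**Shortened treatments per week** at p = 10%: 0.10 × 3 = 0.30 versus 0.10 × 6 = 0.60.

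**Change from baseline** at p = 5% throughout: control 0.65 to 0.65; nocturnal 0.65 to 1.30.

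**Read the other way.** One missed treatment per month is 1/13.0 = 7.7% of sessions in the control arm and 1/26.1 = 3.8% in the nocturnal arm. Equal counts would therefore hide a nocturnal miss probability half that of controls.

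**Effect on a test.** A simulation used 45 patients per arm, 156 and 312 sessions over the year, no dropout, the same beta distribution of p in both arms and a two-sided Mann-Whitney test at 0.05, with 2,000 runs per setting. The test and the spread of p are assumptions; the protocol names neither for these outcomes.

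| Mean p | Beta concentration | Rejected, counts | Rejected, fraction of scheduled |
|---|---|---|---|
| 5% | 5 | 19% | 5.1% |
| 5% | 20 | 78% | 4.7% |
| 10% | 5 | 46% | 4.6% |

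With no difference in adherence, the counts differ significantly far more often than 5% of the time; the fractions hold the nominal level.

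**The case against.** Table 8 is a summary list and states no method of comparison. Section 9.10, which covers compliance, says rates; Section 4.1 uses both a rate and a percentage of scheduled treatments; and the denominator of a descriptive rate can be left to the analysis plan. It is therefore an inference, not a statement in the protocol, that the arms will be compared on raw counts. That much stands. But a number per month is itself a rate, so the word in Section 9.10 does not displace the explicit count in Table 8. The protocol then measures one behavior in ways that do not agree, and the outcome table carries the one that is not comparable between arms.

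Three further limits also stand. Modality change, the only burn-out measure named in Section 5.3 (item d), is a proportion of patients and has no session denominator. The factor of two requires equal per-session probabilities. And the patient burden named in the safety objective (Section 2.1) is not what these counts measure: Table 8 lists it separately, and Section 5.1.5.7 bases its primary assessment on recovery time.

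A reader might go on to infer that intradialytic hypotension has the mirror-image fault, because "The rate of IDHE will be computed as fraction of reported sessions during which IDHE occurred" and the nocturnal arm has twice the sessions. The documents do not support that. The fraction is a clearly defined per-treatment risk, and it fits the Bernoulli model in Section 9.7. Take the protocol's figure of about 20% of sessions on 3 per week and an illustrative 10% on 6 per week. Weekly episodes are then 0.20 × 3 = 0.6 and 0.10 × 6 = 0.6. The per-treatment risk has truly halved and is reported correctly; the weekly figure is a different quantity.

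**Conclusion.** The point holds for the two count measures of burn-out. At any equal per-session probability they are twice as high in the nocturnal arm and rise from baseline there only. The factor of two follows from the prescribed schedules; the absolute counts rest on the assumed 2% to 20%, and the rejection rates on the assumed spread and test.

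The reach is limited. It would be too much to say that burn-out as a whole doubles, that the safety objective on patient burden is compromised, or that the hypotension outcome is biased. The modality-change measure, the co-primary and main secondary outcomes and the power figures do not depend on these counts. What needs correcting is the definition of two risk measures, and its disagreement with the benchmark in Section 4.1.

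**What to change.** In Table 8 and Section 9.10, define missed and shortened treatments as the number missed or shortened divided by the number of sessions scheduled under the randomized assignment, over the same month or week. Show the raw counts descriptively beside the fractions. Naming the assigned schedule matters because Section 3.1.6 foresees nocturnal patients on 5 or 4 sessions per week who are still analyzed as randomized. Form instructions should say against which schedule a session counts as missed.

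The cost is wording. The numerators are already collected (Table 9 F) and the denominator is the prescribed schedule.

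The hypotension definition need not change. A per-patient-week figure may be added as an optional descriptive supplement, from the one-week run-sheet window that Section 6.2.2 records at baseline and months 4, 8 and 12.
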